NON-INTERVENTIONAL (NI) STUDY PROTOCOL

PASS information

Title	An Active Surveillance, Post-Authorization Study to Assess Tofacitinib Utilization Patterns and to Characterize the Safety of Tofacitinib Use in Patients with Moderately to Severely Active Ulcerative Colitis in the Real-World Setting Using Data from a US Administrative Healthcare Claims Database
Protocol number	A3921347
Protocol version identifier	3.0
Date	30 September 2024
HMA-EMA Catalogues of RWD Studies number	EUPAS36041
Active substance	L04AA29 Tofacitinib
Medicinal product	Xeljanz® (tofacitinib)
Product reference	EU/1/17/1178/001-014
Procedure number	EMEA/H/C/004214/X/0005/G
Marketing Authorization Holder(s) (MAH)	Pfizer Europe MA EEIG [name]
Joint PASS	No
Research question and objectives	Research Question 1:

What are the utilization patterns of tofacitinib in the United States (US) with regard to on-label and off-label use?

Objectives:

- To estimate the proportion of tofacitinib users who receive the drug for the approved indications during the study period
- To describe the characteristics of patients who are prescribed tofacitinib for on-label, off-label and unknown indications in terms of the following:
 - Demographics (e.g., age, sex);
 - Comorbidities;
 - Prior and concurrent medications;
 - Prescribed daily dose and duration of tofacitinib therapy
- To estimate the proportion of UC patients on 5 mg twice daily or 11 mg once daily and 10 mg twice daily or 22 mg once daily maintenance therapies
- To estimate the proportion of non-UC patients on 10 mg twice daily or 22 mg once daily therapy
- To estimate the proportion of patients with approved indications who have ≥1 thrombosis risk factors and are prescribed tofacitinib, overall and stratified by dose
- To estimate the proportion of tumor necrosis factor inhibitor (TNFi)-

naïve UC patients prescribed tofacitinib pre and post 01 July 2019

Research Question 2:

What are the incidence rates of safety events of interest (described below) in adult ulcerative colitis (UC) patients treated with tofacitinib (including the immediate-release formulation [dosed as 5 mg and 10 mg twice daily] and the extended-release formulation [dosed as 11 mg and 22 mg once daily]) in the course of routine clinical care?

Primary Objective:

To estimate the incidence rate of malignancy, excluding non-melanoma skin cancer (NMSC), among adult UC patients who initiate tofacitinib in the course of routine clinical care.

Secondary Objective:

To estimate the incidence rates of other safety events of interest, including (but not limited to): lung cancer, lymphoma, NMSC, opportunistic infections (e.g. tuberculosis), major adverse cardiac events (MACE), venous thromboembolism (deep venous thrombosis [DVT] and pulmonary embolism [PE]), myocardial infarction (MI), hepatic events, serious infections, herpes zoster (HZ reactivation), progressive multifocal leukoencephalopathy (PML), gastrointestinal (GI) perforations, interstitial lung disease (ILD), fractures, surgery for UC, and death in adult UC patients who initiate tofacitinib in the course of routine clinical care.

Incidence rates will be estimated among:

Cohort 1: UC patients initiating tofacitinib, overall and stratified by dose (5 mg twice

	daily, 11 mg once daily, 10 mg twice daily, 22 mg once daily) and prior biologic use.
	For contextualization and risk characterization purposes, incidence rates will also be estimated among the following groups:
	Cohort 2: UC patients who initiate biologics, with/without concurrent immunomodulators/immunosuppressants, overall and stratified by TNFi/non-TNFi use and number of previous biologic treatments
	Cohort 3: UC patients who initiate immunomodulators/immunosuppressants without concurrent biologics
	Cohort 4: UC patients naïve to both biologics and immunomodulators/immunosuppressants
Country of study	United States
Author	[name], MPH [name],

Marketing Authorization Holder(s)

Marketing Authorization Holder(s)	Pfizer Europe MA EEIG [name]
MAH contact person	[name]
	Pfizer Ltd
	[name]
	[name]
	[name]
	[name]

Tofacitinib
A3921347 NON-INTERVENTIONAL STUDY PROTOCOI
Version 3.0, 30 September 2024

United Kingdom

This document contains confidential information belonging to Pfizer. Except as otherwise agreed to in writing, by accepting or reviewing this document, you agree to hold this information in confidence and not copy or disclose it to others (except where required by applicable law) or use it for unauthorized purposes. In the event of any actual or suspected breach of this obligation, Pfizer must be promptly notified.

2. LIST OF ABBREVIATIONS

Abbreviation	Definition
6-MP	6-mercaptopurine
ADR	Adverse Drug Reaction
AE	Adverse event
AZA	Azathioprine
CI	Confidence interval
CV	Cardiovascular
CVD	Cardiovascular disease
DD	Daily dose
DMARD	Disease modifying antirheumatic drug
DVT	Deep vein thrombosis
EMA	European Medicines Agency
EU	European Union
GEP	Good Epidemiological Practice
GI	Gastrointestinal
GPP	Guidelines for Good Pharmacoepidemiology Practices
HMA	Heads of Medicines Agencies
HR	Hazard ratio
Hx	History
HZ	Herpes zoster
IBD	Inflammatory bowel disease
ICD	International Classification of Diseases
ICH	International Conference on Harmonization of Technical Requirements for Registration of Pharmaceuticals for Human Use
IEA	International Epidemiological Association
IEC	Independent Ethics Committee
ILD	Interstitial lung disease
ISPE	International Society for Pharmacoepidemiology
IR	Incidence rate
IRB	Institutional Review Board
JAK	Janus kinase
MACE	Major adverse cardiovascular events
MI	Myocardial Infarction
MTX	Methotrexate
NDA	New Drug Application
NI	Non-interventional
NMSC	Non-melanoma skin cancer
NSAIDs	Non-steroidal anti-inflammatory drugs

Abbreviation	Definition
OI	Opportunistic infection
PASS	Post-Authorization Safety Study
pcJIA	Polyarticular-course juvenile idiopathic arthritis
PE	Pulmonary embolism
PML	Progressive multifocal leukoencephalopathy
PsA	Psoriatic arthritis
RA	Rheumatoid arthritis
RMP	Risk management plan
RWD	Real-world data
SAP	Statistical analysis plan
TB	Tuberculosis
TNFi	Tumor necrosis factor inhibitor
UC	Ulcerative colitis
US	United States
USPI	United States prescribing information
VTE	Venous thromboembolism

4. ABSTRACT

Title: An Active Surveillance, Post-Authorization Study to Assess Tofacitinib Utilization
Patterns and to Characterize the Safety of Tofacitinib Use in Patients with Moderately to
Severely Active Ulcerative Colitis in the Real-World Setting Using Data from a US
Administrative Healthcare Claims Database

• **Version:** 3.0

• **Date:** 30 September 2024

• Main author/affiliation: [name], PhD, Pfizer, Inc.

• Rationale and background: Tofacitinib, an inhibitor of the Janus kinase (JAK) family of kinases, was approved in the United States (US) in May 2018 at a dose of 5 mg twice daily or 10 mg twice daily for the treatment of adults with moderate-to-severe ulcerative colitis (UC). In July 2019, the US prescribing information (USPI) was updated to note that tofacitinib should be prescribed for adult patients with moderate-to-severe UC who have had an inadequate response or who are intolerant to tumor necrosis factor inhibitors (TNFis). In December 2019, the extended-release formulation was also approved for UC patients at a dose of 11 mg once daily and 22 mg once daily. Tofacitinib is also currently approved for adult patients with moderate-to-severe rheumatoid arthritis (RA) and active psoriatic arthritis (PsA) at a dose of 5 mg twice daily and 11 mg once daily, as well as at a dose of 5 mg twice daily for patients aged ≥2 years with active polyarticular course juvenile idiopathic arthritis (pcJIA). Due to the potential for off-label use of the 10 mg twice daily and 22 mg once daily dosing regimens in non-UC patients, as well as the potential for use of tofacitinib in non-indicated populations, it would be useful to understand the patterns of post approval use in the US.

In addition, understanding of long-term safety associated with real-world tofacitinib use, including the potential risk of malignancy and other safety events of interest, is needed. Follow-up of large cohorts of patients over a long period can help in the evaluation of any potential risk of malignancy, as well as any other potential safety events of interest, that may be associated with tofacitinib treatment.

To understand the patterns of tofacitinib use in the US, as well as to characterize the risk of safety events of interest that may be associated with its use, Pfizer will implement a post-approval, drug utilization and active surveillance study using a United States (US) administrative healthcare claims database. This non-interventional study is a post-marketing commitment to the US Food and Drug Administration (FDA), and is also designated as a category 3 study in the European Union (EU) risk management plan (RMP).

Research questions: There are two main research questions that will be evaluated:

Research Question 1

What are the utilization patterns of tofacitinib in the US with regard to on-label and off-label use?

Research Ouestion 2

What are the incidence rates of safety events of interest in adult UC patients treated with tofacitinib (including both the immediate-release [5 mg and 10 mg twice daily] and the extended-release [11 mg and 22 mg once daily] formulations) in routine clinical care?

• **Objectives**: The study objectives are described below as follows:

To address the first research question, the objective will be to describe the utilization patterns of tofacitinib in the US with regard to on-label and off-label use by:

- Estimating the proportion of tofacitinib users who receive the drug for the approved indications during the study period
- O Describing the characteristics of patients who are prescribed to facitinib for onlabel, off-label and unknown indications in terms of the following:
 - Demographics (e.g., age, sex);
 - Comorbidities;
 - Prior and concurrent medications:
 - Prescribed daily dose and duration of tofacitinib therapy
- Estimating the proportion of UC patients on 5 mg twice daily or 11 mg once daily and 10 mg twice daily or 22 mg once daily maintenance therapies
- Estimating the proportion of non-UC patients on 10 mg twice daily or 22 mg once daily therapy
- Estimating the proportion of patients with approved indications who have ≥1 thrombosis risk factors and are prescribed tofacitinib, overall and stratified by dose
- Estimating the proportion of TNFi-naïve UC patients prescribed tofacitinib pre and post 01 July 2019

To address the second research question, the objectives will be as follows:

1. To estimate the incidence rate of malignancy, excluding non-melanoma skin cancer (NMSC), among adult UC patients who initiate tofacitinib in the course of routine clinical care, and

- 2. To estimate the incidence rates of other safety events of interest, including (but not limited to) lung cancer, lymphoma, NMSC, opportunistic infections (e.g. tuberculosis), major adverse cardiac events (MACE), venous thromboembolism (VTE; deep venous thrombosis [DVT] and pulmonary embolism [PE]), myocardial infarction (MI), hepatic events, serious infections, herpes zoster (HZ) reactivation, progressive multifocal leukoencephalopathy (PML), gastrointestinal (GI) perforations, interstitial lung disease (ILD), fractures, surgery for UC and death amongadult UC patients who initiate tofacitinib in the course of routine clinical care. For contexualization and risk characterization purposes, incidence rates of these safety events of interest in adult UC patients initiating treatment with other approved systemic agents, as well as adult UC patients naïve to both biologics and immunomodulators/immunosuppressants will also be assessed.
- **Study design**: This is a drug utilization and active surveillance study utilizing secondary data from the International Business Machines (IBM) Watson Health MarketScan® Research Databases, a US administrative healthcare claims database, from November 2012 (time of first of US approval for tofacitinib) through to 30 June 2025 (end of data collection).
- Population: The study population will include all patients enrolled in the Marketscan database during the study period who have received ≥1 prescription of tofacitinib. Additionally, for the active surveillance population (to be used for the estimation of incidence rates for the safety events of interest in adult UC patients as described above), a sub-population will be created which will include adult UC patients aged ≥18 years enrolled in the Marketscan database who are initiating treatment with tofacitinib in the course of routine clinical care (Cohort 1). For contextualization and risk characterization purposes, the study will also include the following treatment cohorts: UC patients who initiate biologics, overall and stratified by TNFi/non-TNFi use and number of previous biologic treatments (Cohort 2); UC patients who initiate immunomodulators/immunosuppressants without concurrent biologics (Cohort 3); UC patients naïve to both biologics and immunomodulators/immunosuppressants (Cohort 4).
- Variables: The study variables will include baseline patient characteristics (i.e., clinical and demographic characteristics, comorbidities, and current and past therapies). To allow for the evaluation of drug utilization patterns, indication for tofacitinib use (classified as on-label, off-label, or unknown) will be characterized, and prescribed daily dose and duration of tofacitinib therapy will also be captured. For the active surveillance portion of the study, the primary safety event of interest is malignancy, excluding non-melanoma skin cancer (NMSC); other key safety events of interest include (but are not limited to) the following: lung cancer, lymphoma, NMSC, serious and opportunistic infections, hepatic events, venous thromboembolism and cardiovascular events, MI, progressive multifocal leukoencephalopathy, gastrointestinal perforations, ILD, fractures, surgery for UC, and death (note that due to database limitations, only in-hospital mortality can be captured).

- Data source: The IBM Watson Health MarketScan® Research Databases, a large US administrative healthcare claims database, will be used as the data source for this analysis. The MarketScan claims databases contain 143 million unique patients since 1996. It is a nationally representative data sample of Americans with employer-provided health insurance, as well as Medicare, and contains complete information on outpatient prescriptions and both inpatient and outpatient diagnoses.
- Study size: This is a descriptive study and all eligible patients during the study period in the Marketscan claims database who have received ≥1 tofacitinib prescription will be included, with no upper limit on the sample size. There are 11,857 patients who have received at least one prescription of tofacitinib in 2016-2018 IBM Marketscan data. Based on the same data, , there are an estimated 59,080 patients with either one inpatient diagnosis of UC, or at least two outpatient diagnoses of UC, with at least one of these two outpatient codes documented by a gastrointestinal specialist.
- Data analysis: This analysis will include descriptive summaries of baseline variables, proportion of tofacitinib users who receive the drug for the approved indications during the study period, and descriptive analysis of patients who are prescribed tofacitinib for on-label, off-label and unknown indications (demographics, comorbidities, prior and current medications, and prescribed daily dose and duration of tofacitinib therapy). Among patients with on-label (approved) indications (i.e. RA, PsA, UC, pcJIA), tofacitinib dose will be assessed, and classified as on-label dose or off-label dose according to each prescription of tofacitinib. The proportion of tofacitinib prescriptions with off-label dosing, stratified by approved indication, will be estimated. To further assess on-label/off-label use of tofacitinib, the proportion of TNFi-naïve UC patients prescribed tofacitinib prior to 01 July 2019 (on-label) and post 01 July 2019 (off-label) will also be estimated and described. Additionally, to further understand off-label dosing among patients with non-UC approved indications such as RA, PsA and pcJIA, the proportions of non-UC patients on 10 mg twice daily/22 mg once daily therapy will also be estimated and reported.

As well, among UC patients specifically, the proportion of UC patients on 5 mg twice daily/11 mg once daily and 10 mg twice daily/22 mg once daily maintenance therapies, as well as the proportion of patients with approved indications (i.e. RA, PsA, UC, pcJIA) with ≥1 thrombosis risk factors who are prescribed tofacitinib (overall and stratified by dose) will also be estimated.

Additionally, incidence rates of the safety events of interest as described above in all study cohorts will be estimated.

• Milestones:

Start of data collection: June 2020¹ End of data collection: June 2025

Interim report 1: June 2022 Interim report 2: June 2024 Final study report: June 2026

¹ This represents start of data collection for the active surveillance portion of the study. Start of data collection for the drug utilization study will be March 2021.

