9.3.2. Definition of On-Label and Off-Label Use for Assessing Utilization Patterns

The following table summarizes the date tofacitinib was approved in the US and the approved dose for each of the three approved indications.

Table 2. Summary of approved indications and dosages for tofacitinib in the US

Indication	Date approved in the US	Approved dose	Limitations for use	
RA	06 Nov 2012	5 mg immediate-release tablets twice daily	Not recommended for use in combination with biologic	
	24 Feb 2016	11 mg prolonged release tablets once daily	DMARDs or potent immunosuppressants such as azathioprine and cyclosporine	
PsA	14 Dec 2017	5 mg immediate-release tablets twice daily	Not recommended for use in combination with biologic DMARDs or potent immunosuppressants such as azathioprine and cyclosporine	
	14 Dec 2017	11 mg prolonged release tablets once daily		
UC	30 May 2018	5 mg or 10 mg immediate- release tablets twice daily	Not recommended for use in combination with biological	
	12 December 2019	11 mg or 22 mg prolonged release tablets once daily	therapies for UC or potent immunosuppressants such as azathioprine and cyclosporine	
рсЛА	25 September 2020	5 mg immediate-release tablets twice daily or weight-based equivalent twice daily (tablet or oral solution)	Not recommended for use in combination with biologic DMARDs or potent immunosuppressants such as azathioprine and cyclosporine	

pcJIA = polyarticular course juvenile idiopathic arthritis; PsA = psoriatic arthritis; RA = rheumatoid arthritis; UC = ulcerative colitis; US = United States

To evaluate indication for use, all patients' to facitinib use will be classified as onlabel indication, off-label indication or unknown indication associated with the first to facitinib prescription during the observation period. Thus, for the purpose of this analysis, on-label indication for use of tofacitinib will be defined, based on the date of the first prescription, as a prescription of the drug to:

- 1. An adult (patients aged ≥18 years), AND
- 2. After November 2012, a patient whose first tofacitinib prescription occurred after a diagnosis of RA (defined as either as having ≥ 1 inpatient or ≥ 2 outpatient RA diagnosis codes on two unique calendar days, with at least one from a rheumatologist), OR

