- 3. After December 2017, a patient whose first tofacitinib prescription occurred after a diagnosis of PsA (defined as either as having ≥ 1 inpatient or ≥ 2 outpatient PsA diagnosis codes on two unique calendar days, with at least one from a rheumatologist), OR
- 4. Between May 2018 and July 2019, a patient whose first tofacitinib prescription occurred after a diagnosis of UC (defined as the first UC diagnosis code from an inpatient visit or after the second UC diagnosis code from an outpatient visit), OR
- 5. After July 2019, a patient whose first tofacitinib prescription occurred after a diagnosis of UC (as defined above) AND after evidence of prior TNFi use (i.e. using all available data, a prescription for ≥1 TNFi agent prior to first tofacitinib prescription), OR
- 6. After September 2020, a patient aged ≥2 years whose first tofacitinib prescription occurred after a diagnosis of pcJIA (defined as either as having ≥ 1 inpatient or ≥ 2 outpatient pcJIA diagnosis codes on two unique calendar days, with at least one from a rheumatologist)

In contrast, off-label indications will be defined as use of tofacitinib among patients with other diagnoses (i.e. lack of diagnosis codes for RA, PsA, UC or JIA) not fulfilling any of the conditions outlined above. If off-label use among non-approved indications occurs, it is expected that tofacitinib will be more likely used among patients with other non-approved rheumatic conditions (e.g. psoriasis, ankylosing spondylitis) or other non-approved IBD conditions (e.g. Crohn's disease). Thus off-label indications will be identified by broadly targeting diagnosis codes for other non-approved rheumatic and IBD conditions. Additionally, if the indications for which tofacitinib is prescribed cannot be determined from the available data, these will be classified as unknown indications and will evaluated separately as described in Section 9.7.1.

Among patients with on-label indications, to facitinib dose will be assessed. For each of these patients, every to facitinib prescription will be classified as on-label or off-label based on the labeled dose for the patient's indication at the time of prescription. Thus, for the

purposes of this analysis, on-label dose of tofacitinib will be defined, based on each tofacitinib prescription, using the following criteria:

- 1. Between November 2012 and November 2017, a prescription of tofacitinib 5 mg twice daily occurring only after a diagnosis of RA (as defined above)

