- 2. Between February 2016 and November 2017, a prescription of tofacitinib 11 mg once daily occurring only after a diagnosis of RA (as defined above)
- 3. After December 2017, a prescription of tofacitinib 5 mg twice daily or 11 mg once daily occurring only after a diagnosis of either RA or PsA (as defined above)
- 4. After May 2018, a prescription of tofacitinib 5 mg twice daily occurring only after a diagnosis of either RA, PsA or UC (as defined above)
- 5. After May 2018, a prescription of tofacitinib 10 mg twice daily occurring only after a diagnosis of UC (as defined above)
- 6. After December 2019, a prescription of tofacitinib 11 mg once daily or 22 mg once daily occurring only after a diagnosis of UC (as defined above)
- 7. After September 2020, a prescription of tofacitinib 5 mg twice daily occurring only after a diagnosis of RA, PsA, UC or pcJIA.

For each approved indication of tofacitinib (i.e. RA, PsA, UC, pcJIA), the proportion of tofacitinib prescriptions with off-label dosing will be estimated as described in Section 9.7.1.

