9.3.6. Endpoints of Interest

To assess tofacitinib utilization patterns, the main endpoint of interest to be captured in the interim and final study reports will be the indication for tofacitinib use, classified as on-label, off-label, or unknown, based on medical events (diagnoses and/or medication use) identifiable around the time of the first ever tofacitinib prescription. The date of first prescription of tofacitinib during the study period is the index date as described in Section 9.3.4.1. All patients' tofacitinib use will be classified as on-label indication, off-label indication or unknown indication according to the first prescription of tofacitinib received, regardless of later prescriptions. The on-label, off-label and unknown indication classifications will be made based on the authorized indication(s) as of the index date.

For the active surveillance portion of the study, the safety events of interest (to be defined via ICD-code based algorithms in the SAP) which will also be captured in the interim and final study reports include the following:

- Malignancy, excluding NMSC
- Lung cancer
- Lymphoma
- NMSC
 - Serious infections
 - Opportunistic infections (e.g. tuberculosis)
 - HZ reactivation

- MACE
- VTE (DVT and PE)
- Myocardial Infarction (MI)
- Hepatic events
- PML (PML)
- GI perforations
- ILD
- Fractures
- Surgery for UC (e.g. colectomies, partial colectomies, and proctocolectomies; full list of procedures to be detailed in SAP)
- Death

Of note, due to limitations related to the Marketscan database, only in-hospital deaths can be captured (outcome will be defined via an algorithm currently under development, details of which will be outlined in the SAP). Deaths occurring in other environments such as home, non-hospital institutions, etc., cannot be captured.

The above list of safety endpoints may be extended with additional sub-diagnoses or new health-related outcomes as agreed to by study researchers and Sponsor before the interim reports and final study report. These decisions will be made prior to initiation of analyses and documented in the SAP kept on file by the Sponsor.

In addition, the final study report will include the number of tofacitinib-exposed pregnancies.

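### The on-label lists in Section 9.3.2 end at September 2020, while the protocol's own rule follows the label in force up to 30 June 2025, and nothing says which governs

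*Protocol*

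**What the plan says.** **The general rules.** Protocol Section 9.3.6 states: "The on-label, off-label and unknown indication classifications will be made based on the authorized indication(s) as of the index date". The index date of the drug utilization study is the first tofacitinib prescription in the study period (Section 9.3.4.1), and eligible prescriptions run to 30 June 2025 (Section 9.5). Section 9.3.2 adds a parallel rule for dose: each prescription is judged against the dose labelled for the patient's indication when it was prescribed.

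**The operative lists.** Section 9.3.2 then defines both classifications by numbered items, introduced as the definitions for this analysis.
- The last indication item is "After September 2020, a patient aged ≥2 years whose first tofacitinib prescription occurred after a diagnosis of pcJIA".
- The last dose item is "After September 2020, a prescription of tofacitinib 5 mg twice daily occurring only after a diagnosis of RA, PsA, UC or pcJIA".
- The last approval date in Table 2 is "25 September 2020".

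The abstract, Sections 9.1 and 9.3.2, and Section 9.7.1 repeat RA, PsA, UC and pcJIA as the complete set of approved indications, as in "Among patients with on-label (approved) indications (i.e. RA, PsA, UC, pcJIA), tofacitinib dose will be assessed".

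**Off-label targets.** Section 9.3.2 expects off-label use mainly in other "non-approved rheumatic conditions (e.g. psoriasis, ankylosing spondylitis") and in non-approved IBD conditions, with Crohn's disease as the example.

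**Currency of the text.** Version 3.0 is dated 30 September 2024. Its abstract says "Tofacitinib is also currently approved for adult patients with moderate-to-severe rheumatoid arthritis (RA") and goes on to PsA and pcJIA. Section 7 likewise describes three further current indications besides UC.

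**The concern.** The same classification is specified in two ways. One follows the label over time; the other is a list that stops at a fixed point. A programmer who codes the numbered items cannot register a label revision after September 2020. A programmer who codes Section 9.3.6 must look beyond the items. The text does not say who is right, and it provides no step for checking the lists against the label up to the end of data collection.

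If the label did change, the direction of the error would depend on the change. A new indication would be counted as off-label, and its users would drop out of the dose assessment, which is limited to patients with an on-label indication. A new restriction on an existing indication would leave its users counted as on-label. The protocol itself treats restrictions as decisive: the July 2019 change moves TNFi-naïve UC starters from on-label to off-label (Sections 9.3.2 and 9.7.1). Either error would fall on the most recent starters.

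**Working it through.** The protocol gives no figure on this point to reproduce. The check consists of date arithmetic and a comparison of sections.

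**1. The period without a dated entry.** Inputs: first US approval 6 November 2012 and last list date 25 September 2020 (Table 2); end of data collection 30 June 2025 (Section 9.5); version date 30 September 2024.
- Whole index window: 6 Nov 2012 to 30 Jun 2025 = 4,619 days.
- After the last list entry: 25 Sep 2020 to 30 Jun 2025 = 1,739 days, and 1,739 / 30.4375 = 57.1 months. Share: 1,739 / 4,619 = 37.6%.
- If the 2024 text counts as a check of the label: 30 Sep 2024 to 30 Jun 2025 = 273 days, and 273 / 30.4375 = 9.0 months. Share: 273 / 4,619 = 5.9%.

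These are shares of calendar time. They are not error rates.

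**2. What the error would be.** For the overall on-label proportion:

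error = (share of first prescriptions dated after a label change) × (share of those whose class the change alters).

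The documents supply neither factor. They record no US label change after September 2020, and the only counts in Section 9.5 are for 2016 to 2018. With no change the error is zero. With a change it cannot exceed the share of first prescriptions dated after it. No narrower range follows from the documents.

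**3. Rule against list.**

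| Item | Label-in-force rule | Operative text |
|---|---|---|
| Indication | Section 9.3.6: authorization at the index date | Section 9.3.2: six numbered items, last dated September 2020 |
| Dose | Section 9.3.2: labelled dose at prescription | Section 9.3.2: seven numbered items, last dated September 2020 |
| End of period | 30 June 2025 | No closing date and no check of the label |
| Which prevails | Not stated | Not stated |

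**4. Do the pieces of Section 9.3.2 agree with each other now?** Not fully.
- The sentence above Table 2 speaks of "the approved dose for each of the three approved indications", but the table has four.
- Table 2 has no entry for the July 2019 UC restriction, although the indication items apply it.
- For pcJIA, Table 2 gives 5 mg twice daily or a weight-based equivalent as tablet or oral solution. The last dose item gives only 5 mg twice daily. A weight-based pcJIA prescription would be on-label under the table and off-label under the item. These places must be reconciled.

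**The case against.** The strongest reply is that a dated list conflicts with Section 9.3.6 only if the label changed after the last entry, and no part of the protocol says it did. That stands. A reader might infer that recent users are in fact being misclassified; the documents do not support this.

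Second, a reader might infer that the lists are 57 months out of date. The 30 September 2024 text calls the four indications current, and the amendment log shows the abstract as revised in version 3.0. On that reading only about 9 months are uncovered. The log does not list Sections 7, 9.3.2 or 9.7.1 as changed in version 3.0, but this silence shows neither that the lists were rechecked nor that they were not.

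Third, a reader might infer that psoriasis, ankylosing spondylitis and Crohn's disease are fixed as off-label for the whole period. They are examples, and the operative word is non-approved. A condition that gained approval would no longer fit.

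Fourth, the count of three indications above Table 2 is a slip in a lead-in. Both operative lists include pcJIA, so the slip does not show that the classification itself lags.

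Fifth, Section 9.3 leaves detailed definitions to the SAP, and Section 9.7 lets the SAP modify plans. A lookup table could well sit there. But Section 9.3.2 fixes these criteria itself, and Section 9.7 says major changes to endpoint definitions would be reflected in a protocol amendment. The protocol should therefore at least state which rule prevails.

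**Conclusion.** The point holds as a conflict of rules for the main utilization endpoint and for the dose classification that depends on it. The closed lists carry out the label-in-force rule only on the assumption that no relevant US label change took effect between their last entry and 30 June 2025. The protocol neither states that assumption nor provides for checking it.

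The numerical effect is unknown and may be zero. The uncovered period is 37.6% of the index window counted from the last entry, or 5.9% if the 2024 text is accepted as a check. Neither figure says how many patients would be affected.

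The pcJIA dose discrepancy between Table 2 and the dose list does not depend on any later label change. It affects the proportion of pcJIA prescriptions classed as off-label dosing whenever weight-based regimens occur. Overall this is an inexpensive improvement to the specification, with no error in results demonstrated.

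**What to change.** 1. State in Section 9.3.2 that the label-in-force rule (Section 9.3.6 for indication, the time-of-prescription rule in 9.3.2 for dose) governs where it differs from the numbered items.
2. Verify Table 2 and both lists against every US label revision of indication, population restriction and regimen through 30 June 2025, and record the verification date.
3. Turn Table 2 into a dated table that includes restrictions such as that of July 2019. Classify each first prescription (indication) and each prescription (dose) by the row in force on that date.
4. Have the abstract, Section 9.1 and Section 9.7.1 refer to that table in place of the four-indication list.
5. Treat a condition as an off-label target only for dates on which it was not approved.
6. Reconcile the pcJIA regimen between Table 2 and the dose list, and correct the count of indications above Table 2.

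The cost is protocol or SAP wording and a lookup table in the program, before the final report due 30 June 2026. No new data are needed. If the label did not change, the indication results stay as they are, and only the pcJIA dose classification could move once its two definitions are reconciled.
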